5.3 Exclusion Criteria

1. Patients whose EUS diagnosis indicated non-submucosal tumors (i.e., not consistent with submucosal tumors/subepithelial lesions).

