2.1 Primary Objective

To identify factors associated with the coincidence (concordance) between EUS diagnosis and pathological diagnosis for colorectal subepithelial lesions.

3. Endpoints

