3.1 Primary Endpoint

Coincidence rate between EUS diagnosis and pathological diagnosis.

4. Study Design

This is a single-center, retrospective, observational study. All patients who underwent colorectal EUS at Shenzhen Hospital of Southern Medical University between 2015 and 2023 will be screened, and their endoscopy/EUS reports and pathology reports will be retrospectively reviewed and analyzed.

If a patient had two or more colorectal lesions evaluated by EUS, lesions at different sites will be treated as independent EUS examinations. Only SEL cases with histopathologic confirmation will be included for further analysis.

During the study, no randomization will be performed and no protocol-driven treatment will be administered or provided. When clinically indicated, treatment decisions and treatment selection will be made at the discretion of the treating physician.

5. Study Population

The study population consists of patients with colorectal subepithelial lesions.

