5.2 Inclusion Criteria

1. Patients admitted to Shenzhen Hospital of Southern Medical University from 2015 to 2023 who underwent colorectal EUS.
2. Patients diagnosed with colorectal submucosal tumors (subepithelial lesions) according to the Chinese expert consensus on endoscopic diagnosis and treatment of gastrointestinal submucosal tumors (2023 edition) and related criteria.

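### Exclusion 5.3(1) selects on the EUS call, so the concordance rate and factor analysis apply only to lesions EUS called SEL, while the plan describes colorectal SELs in general

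*Combined protocol and SAP*

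**What the plan says.** The document title promises the diagnostic accuracy of EUS for colorectal SELs. The primary objective (2.1) is "To identify factors associated with the coincidence (concordance) between EUS diagnosis and pathological diagnosis for colorectal subepithelial lesions". The endpoint (3.1) is "Coincidence rate between EUS diagnosis and pathological diagnosis". Section 5 states: "The study population consists of patients with colorectal subepithelial lesions". None of these limits the target to lesions that EUS itself called SEL.

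Section 4 screens all colorectal EUS patients from 2015 to 2023 and says that "their endoscopy/EUS reports and pathology reports will be retrospectively reviewed and analyzed". It then restricts the analysis: "Only SEL cases with histopathologic confirmation will be included for further analysis". It counts by lesion, in that "lesions at different sites will be treated as independent EUS examinations".

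Inclusion criterion 5.2(2) admits "Patients diagnosed with colorectal submucosal tumors (subepithelial lesions) according to the Chinese expert consensus" and related criteria, without saying whether EUS or pathology makes the diagnosis. The single exclusion, 5.3(1), is worded per patient: "Patients whose EUS diagnosis indicated non-submucosal tumors". Section 6.1 enrols those who meet the criteria, and 6.3 extracts data for enrolled participants. Section 10.2 lists case distribution without defining it. Section 10.3 compares concordant with non-concordant cases by ANOVA and logistic regression.

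**The concern.** When the result of the test under study decides who enters the analysis, one kind of error cannot appear in the results. Here it is the missed SEL: pathology says SEL, EUS said otherwise. Each such lesion is a disagreement, and 5.3(1) takes it out of the denominator of the rate and out of the non-concordant group in 10.3.

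The rate matters because it is the primary endpoint. The factor analysis matters more because it is the primary objective: a feature that makes EUS miss SELs may show no association with concordance if the misses are gone before the comparison is made. A reader of the planned report could not judge either effect, since no section asks for the number of lesions removed in this way.

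**Working it through.** **1. Where each kind of lesion goes (all with pathology)**

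| EUS call | Pathology | As written |
|---|---|---|
| SEL | SEL | In; concordant if the diagnoses agree |
| SEL | not SEL | Unclear: section 4 does not say whether a refuted SEL call counts as histopathologically confirmed |
| not SEL | SEL | Out by 5.3(1), though discordant by definition |
| not SEL | not SEL | Out, and outside any SEL target |

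No section restores or requires a count of the third row.

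**2. Inputs**

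- Illustrative reported rates r: the ends of the 43%–79% range in section 1 (gastrointestinal, not specifically colorectal) and its midpoint, (43 + 79)/2 = 61%.
- n = 269 from section 10.1, used only as a scale for sampling error. It reproduces as an F test with effect size 0.25, 10 numerator and N − 2 denominator degrees of freedom (power 0.8003). The point does not depend on it.
- a = missed SELs divided by included lesions; f = false SEL calls as a share of included lesions. The documents give neither, so all values are assumptions.

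**3. Partial effect on the rate**

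Set included lesions to 1, of which r are concordant. Restoring the missed SELs adds a to the denominator and nothing to the numerator, giving r/(1+a). For example, 0.79/1.05 = 0.752.

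| r | a = 5% | a = 10% | a = 15% |
|---|---|---|---|
| 79% | 75.2% | 71.8% | 68.7% |
| 61% | 58.1% | 55.5% | 53.0% |
| 43% | 41.0% | 39.1% | 37.4% |

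**4. Against sampling error**

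The half-width is h = 1.96 × √(r(1−r)/269), which is 4.9, 5.8 and 5.9 points at 79%, 61% and 43%. At a = 5% the shifts are 3.8, 2.9 and 2.0 points, all inside. The shift exceeds h only when a > h/(r−h): 6.6%, 10.6% and 16.0%, or about 18, 29 and 43 missed lesions beside 269.

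**5. Share of discordant lesions absent from the factor analysis**

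This is a/(1−r+a). At r = 61% it is 11%, 20% and 28% for a = 5%, 10% and 15%. At 79% it is 19%, 32% and 42%; at 43%, 8%, 15% and 21%.

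**6. Net direction**

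If false SEL calls are kept in the planned set, the rate among pathology-proven SELs is r/(1−f+a). With r = 61% and a = 5%:

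- f = 0: 0.61/1.05 = 58.1%
- f = 5%: 0.61/1.00 = 61.0%
- f = 10%: 0.61/0.95 = 64.2%

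The reported 61% would be too high, equal or too low respectively for the pathology-SEL population.

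**7. Patient-level wording**

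Read literally, 5.3(1) also removes a patient's other lesions, including SELs that EUS called correctly. If k such lesions were concordant at rate r, restoring them gives (r + kr)/(1 + k) = r, so the rate does not move. Another mix could move it either way.

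**8. Factor analysis, assumed example**

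Suppose concordance among EUS-called SELs is 70% for both small and large lesions, with no false calls. The planned odds ratio for size is 1.00. If EUS misses 15% of small and 2% of large pathology-proven SELs:

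- small: 0.70 × 0.85 = 0.595, odds 0.595/0.405 = 1.469
- large: 0.70 × 0.98 = 0.686, odds 0.686/0.314 = 2.185
- odds ratio 2.185/1.469 = 1.49

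With 10% and 2% missed it is 1.28. If misses are unrelated to the factor, little changes: with 5% missed in both groups and concordance of 65% and 75%, the odds ratio goes from 1.62 to 1.54.

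**The case against.** The strongest reply is that the study is about something narrower. Section 1 describes EUS characterising SELs to help predict their pathology, and 5.1 and 5.2 define the diagnosis by a consensus on endoscopic diagnosis. On that reading 5.3(1) is simply the complement of 5.2(2), and the target is agreement among EUS-diagnosed SELs. For that target the exclusion is not a bias. This stands, and it is a sensible target. But the title, objective, population and endpoint do not declare it, and 5.2(2) does not say which test decides. The cited consensus might settle that last point, but it cannot be checked here.

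It can also be said that lesions are not necessarily lost from sight: section 4 has the reports of all screened patients reviewed, case distribution could include exclusions by reason, and treating lesions as independent examinations allows a per-lesion reading of 5.3(1). All of this is possible. None of it is required, so the accurate statement is that no count is required, not that one is ruled out.

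Finally, no size comes from the documents. That is correct: a and f are unknown, and at an assumed a of 5% the shift is within sampling error at all three rates.

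**Conclusion.** The plan should be changed. Followed exactly, 5.3(1) gives a rate and factor estimates for lesions that EUS called SEL, while the plan announces results for colorectal SELs in general; the discordant lesions that separate the two are neither analysed nor required to be counted.

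The size is unknown. Other features fixed, the exclusion raises the rate by r − r/(1+a): 2.0 to 3.8 points over the three illustrative rates at an assumed a of 5%, and nothing if a is zero.

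A reader might infer that the reported rate will be too high. The documents do not support that: if refuted SEL calls are kept, they can cancel or reverse the effect, and section 4 does not say whether they are. A reader might also infer that the factor analysis is shown to be wrong. It is not. A factor that drives misses could appear null, but the documents do not show that any factor does, and the odds ratios above rest on assumed miss rates.

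**What to change.** 1. Apply 5.3(1) per lesion, matching section 4.
2. State in section 4 that histopathologic confirmation means that a pathology result is available, whatever it shows. SEL calls that pathology refutes then stay in as non-concordant.
3. Name the primary set as EUS-diagnosed SELs with pathology, and restate the title, population and endpoint to match.
4. From the records already screened, extract lesions that EUS called non-SEL but pathology shows to be SEL, and report their number. Give the coincidence rate and repeat the logistic regression in the pathology-SEL set, with these lesions counted as non-concordant. Section 6.3 must allow this extraction.

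The union of EUS-SEL and pathology-SEL lesions should not be the primary endpoint set. Its membership still depends on the EUS result, and its rate is neither agreement among EUS-called SELs nor agreement among pathology-proven SELs.

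The cost is modest: a wording amendment with ethics committee approval (11.3, 12.1) and some extra extraction. All colorectal EUS patients are already screened, and both diagnoses are listed items in 6.4. The downsides are a second rate that may be less favourable, and recovery only of missed SELs that had pathology in routine care, since the study adds no assessments.

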5.4 Withdrawal and Loss to Follow-up

All enrolled participants have the right to withdraw from this study at any time.

Reasons for withdrawal include:

- Participant requests withdrawal and does not wish to continue participation;
- Participant is lost to follow-up;
- Participant refuses further follow-up;
- Other reasons deemed by the investigator to make the participant unsuitable to continue in the study.

Participants who withdraw during the study will be considered dropouts. After dropout, efforts should be made to contact the participant to complete assessments as feasible and to complete the study summary page.

6. Methods and Procedures

As this is an observational study, no additional study visits, laboratory testing, or assessments beyond routine clinical practice are required. Treating physicians will determine clinical management according to product labeling and local standards of care. Investigators will review medical history and laboratory reports and determine eligibility based on the inclusion and exclusion criteria.

A waiver of informed consent will be requested because the samples and information are derived from medical records and specimens collected during routine clinical care; the study poses no more than minimal risk to participants; the waiver

will not adversely affect participants' rights or welfare; obtaining consent would make the study impracticable; and participants' privacy and personal identifiers will be protected.

The number and timing of clinical visits will be determined by physicians according to local routine practice.

6.1 Informed Consent and Enrollment

A waiver of written informed consent will be applied for. Participants who meet all other inclusion/exclusion criteria will be considered enrolled.

6.2 Participant Identification Number

Each participant will be assigned a unique identification number in chronological order based on the date of examination. All study documents (e.g., case report forms, clinical records) will use this identification number. In accordance with data privacy regulations, the identification number must not include combinations that could identify the participant (e.g., initials plus date of birth should not be used together).

6.3 Data Source / Data Collection Process

Study data will be obtained by extracting routine clinical medical records of enrolled participants. Investigators will enter information from source medical records into study record forms throughout the monitoring period.

6.4 Data Collection Items

1. Demographics: age, sex, initials;
2. Lesion location and size (maximum diameter);
3. EUS echogenic features, layer-related characteristics, EUS diagnosis (primary diagnosis), operator, and device information;
4. Pathology acquisition method, pathological layer, and pathological diagnosis.

7. Criteria for Study Termination / Suspension

7.1 The sponsor has the right to terminate or suspend the study. Before termination/suspension, the sponsor must notify the investigator, the ethics committee, and relevant regulatory authorities and provide the rationale. If the study is terminated/suspended early, restarting the study requires ethics committee approval.

7.2 Termination or suspension as required by the ethics committee.

8. Study Completion

The study will be completed when data collection reaches the predefined time interval.

9. Data Management

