10.1 Sample Size Determination

This is a single-center, retrospective, observational study. One-way analysis of variance (ANOVA) will be used to explore factors associated with concordance versus non-concordance between EUS diagnosis and pathological diagnosis. Using G*Power (version 3.1.9.7) with an effect size of 0.25, $\alpha = 0.05$, power $(1-\beta) = 0.80$, 10 predictors, and 2 groups, the required sample size was calculated to be 269 cases.

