10.3 Statistical Software and General Requirements

- Statistical analyses will be performed using SPSS.
- Continuous variables will be summarized using mean, standard deviation, median, minimum, and maximum values.
- Categorical variables will be summarized using frequencies and percentages.
- One-way ANOVA will be used to evaluate differences in potential factors between the concordant and non-concordant groups.
- Multivariable logistic regression will be performed to identify key factors independently associated with diagnostic concordance.

11. Study Management

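### Concordance is not analysed by how pathology was obtained, so specimen error could lower the coincidence rate or look like a factor in EUS concordance

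*Combined protocol and SAP*

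**What the plan says.** The endpoint in section 3.1 is a single rate: "Coincidence rate between EUS diagnosis and pathological diagnosis". The only condition on the reference standard is in section 4 (Study Design): "Only SEL cases with histopathologic confirmation will be included for further analysis". No section says which specimen types are acceptable, ranks them, or says what happens to a sample that gives no diagnosis.

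Section 6.4 collects "Pathology acquisition method, pathological layer, and pathological diagnosis". Recording the acquisition method implies that more than one method is expected.

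Section 10.3 plans the univariable step as follows: "One-way ANOVA will be used to evaluate differences in potential factors between the concordant and non-concordant groups". A multivariable logistic regression comes next. The candidate factors are not named there. Section 10.1 gives only their number: "10 predictors, and 2 groups, the required sample size was calculated to be 269 cases". Neither section stratifies by acquisition method or plans a sensitivity analysis on it.

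**The concern.** Concordance is a comparison of two readings, and the plan treats the pathology reading as equally reliable however the tissue was taken. A partial sample of a lesion lying beneath the epithelium may miss representative tissue in a way that a whole-lesion specimen does not. When such a sample is wrong and EUS is right, the case is scored as discordant and the discordance is charged to EUS.

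Two results are exposed. The pooled coincidence rate, which is the primary endpoint, can be too low. The factor analysis, which is the primary objective, can return acquisition method as a factor when it reflects the quality of the reference and not the performance of EUS.

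A separate point concerns pathological diagnosis. Concordance is computed from it, and nothing in the plan keeps it out of the model as a predictor.

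**Working it through.** **1. The plan's own figure.** Section 10.1 gives effect size f = 0.25, α = 0.05, power 0.80, 10 predictors and 2 groups. Take a noncentral F test with numerator df 10, denominator df N − 2 and noncentrality f²N. At N = 269 the noncentrality is 0.0625 × 269 = 16.81 and the power is 0.8003. This is the smallest N that reaches 0.80, so 269 is reproduced. With 9, 8 or 7 predictors the same formula gives 259, 248 or 237, so removing a predictor would not make 269 too small on the plan's own method.

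**2. Inputs for the illustration.**
- c, the true EUS accuracy, is the same for all specimens. Section 1 cites 43%–79% for gastrointestinal lesions.
- e, the error in partial samples, is 10–30%. This is an assumption.
- m, the chance that EUS and a partial sample agree when both are wrong, is 20%. This is an assumption.
- b, the share of lesions with a partial sample only, is 10–40%. This is an assumption.
- Whole-lesion pathology is taken as correct, and errors in partial samples as independent of EUS correctness. Both are assumptions.

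**3. Formulas.**
- Observed concordance in partial samples: o = c(1 − e) + (1 − c)em
- Pooled rate: (1 − b)c + bo
- Spurious odds ratio, whole-lesion against partial: [c/(1 − c)] / [o/(1 − o)]

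**4. Odds ratios.** At c = 0.75 and e = 0.10, o = 0.675 + 0.25 × 0.10 × 0.20 = 0.680, and the odds ratio is 3/(0.680/0.320) = 1.41. The other cells follow in the same way.

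| EUS accuracy c | e = 10% | e = 20% | e = 30% |
|---|---|---|---|
| 43% | o = 0.398, OR 1.14 | o = 0.367, OR 1.30 | o = 0.335, OR 1.50 |
| 60% | o = 0.548, OR 1.24 | o = 0.496, OR 1.52 | o = 0.444, OR 1.88 |
| 75% | o = 0.680, OR 1.41 | o = 0.610, OR 1.92 | o = 0.540, OR 2.56 |
| 79% | o = 0.715, OR 1.50 | o = 0.640, OR 2.11 | o = 0.566, OR 2.89 |

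**5. Pooled rate.** At c = 75% the mild end (b = 10%, e = 10%) gives 0.9 × 0.75 + 0.1 × 0.68 = 74.3%. The severe end (b = 40%, e = 30%) gives 0.6 × 0.75 + 0.4 × 0.54 = 66.6%. At c = 43% the same two corners give 0.9 × 0.43 + 0.1 × 0.398 = 42.7% and 0.6 × 0.43 + 0.4 × 0.335 = 39.2%.

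**6. Direction.** Under independence, o is below c whenever (1 − c)m < c. That holds for every m if c exceeds 0.5. At c = 0.43 it holds for m below 0.43/0.57 = 0.75. The downward direction therefore does not hinge on the 20% chosen for m.

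**7. Would it be noticed?** Take N = 269 with 35% partial samples (assumed), e = 20% and m = 20%. An unadjusted two-sided comparison at 0.05 would call acquisition method significant with probability about 0.17 at c = 43%, 0.375 at 60% and 0.75 at 79%. With e = 10% these fall to about 0.07, 0.13 and 0.29.

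**The case against.** The strongest reply is that the documents state very little of this. Neither biopsy nor resection is mentioned anywhere. The specimen mix is unknown, and if nearly all lesions had whole-lesion pathology the effect would be negligible; even the mild corner above moves the rate by only 0.7 points. A wrong sample also costs EUS nothing when EUS was already wrong and the two do not happen to agree. The restriction to histopathologically confirmed cases may already remove some non-diagnostic samples. All of this stands, and it is why the size is given only as an illustration. It does not deal with samples that give a diagnosis but the wrong one.

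A reader might infer from the item count that pathology-side variables must be among the 10 predictors. Leaving out initials, section 6.4 has two demographic items, two lesion items ("Lesion location and size (maximum diameter") and five EUS items ("EUS echogenic features, layer-related characteristics, EUS diagnosis (primary diagnosis), operator, and device information"), which makes nine. Dropping only the two diagnoses from the full list of twelve leaves exactly ten, including acquisition method and pathological layer. The documents do not support that inference. Section 6.4 is a data-collection list, section 10.3 does not refer to it, and several entries are plural. Section 1 itself names margins, homogeneity and acoustic shadowing as separate features; entering those three in place of one echo item turns nine into eleven with no pathology item. The 10 also acts as numerator degrees of freedom in the calculation that gives 269, so one multi-category variable could use several.

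A reader might also infer that pathological layer is circular. It is not part of the endpoint, which compares diagnoses only. Pathological diagnosis is a component of the endpoint. So is EUS diagnosis, although that one is known at the time of the EUS reading.

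Finally, the objective in section 2.1 concerns factors associated with concordance, so acquisition method is a legitimate association to report. That is fair. The matter is how it is interpreted, and it need not be barred.

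**Conclusion.** The point holds as a cheap improvement, not as a demonstrated bias. Followed as written, the plan pools specimens of possibly unequal reference quality into one rate and one model, although it records the variable needed to examine this. If partial samples carry 10–30% error that is independent of EUS correctness, with a 20% chance match, the spurious odds ratio is about 1.1–1.5 at 43% EUS accuracy and 1.4–2.6 at 75%, and the pooled rate is generally biased downward. The effect is material mainly when the error is about 10–20% or more and partial samples are a substantial share; the documents give neither figure. If EUS and pathology errors are correlated, the direction is not assured.

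It is not established that any pathology-side item is among the 10 predictors, or that pathological layer determines the outcome. What is established is that the plan says nothing to exclude pathological diagnosis, from which the outcome is computed.

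**What to change.** In section 10.3:

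1. Report the coincidence rate by acquisition method alongside the pooled rate.
2. Repeat the rate and the multivariable model in lesions with whole-lesion pathology, as a pre-specified sensitivity analysis.
3. Count non-diagnostic samples as unverified, not as discordant, and report how many there are.
4. Do not enter pathological diagnosis as a predictor of EUS performance. Concordance by pathological diagnosis can be tabulated descriptively.
5. If acquisition method is in the model, state that its coefficient may reflect the quality of the reference standard.

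The cost is a few sentences and one repeat analysis on a variable already listed in section 6.4. No new data are needed and the stated 269 need not change. The whole-lesion subset will be smaller, so less precise, and may differ in case mix (lesion size and type). A difference between the two analyses should therefore not be read as reference error alone.
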